Rumah Sakit Ibu & Anak
STELLA MARIS
Women's & Children's Hospital
KLINIK BAYI TABUNG HALIM FERTILITY CENTER
[name]
Telp : [name], [contact]

Efficacy of Platelet-Rich Plasma on Blastocyst Formation in ICSI Cycles Involving Low-Quality Sperm: A Randomized Study

Protocol Version:

Version 1.0

Document Date:

November 17, 2022

Sponsor / Study Site:

Halim Fertility Center, Stella Maris Women's and Children's Hospital, Medan, Indonesia

Ethics Approval Number:

608.1/Dir/RSIA.SM/XII/2022

Principal Investigator:

[name]

Rumah Sakit Ibu & Anak
STELLA MARIS
Women's & Children's Hospital
KLINIK BAYI TABUNG HALIM FERTILITY CENTER
[name]
Telp : [name], [contact]

Study Protocol and Statistical Analysis Plan

Efficacy of Platelet-Rich Plasma on Blastocyst Formation in ICSI Cycles Involving Low-Quality Sperm: A Randomized Study

1. Background and Rationale

Platelet-rich plasma (PRP) is an autologous concentration of platelets containing growth factors that promote tissue regeneration and reduce oxidative stress. Poor sperm quality, particularly in severe oligoasthenoteratozoospermia (SOAT), is associated with impaired fertilisation, reduced embryo development, and lower blastocyst formation rates in intracytoplasmic sperm injection (ICSI) cycles.

Previous findings suggest that PRP improves sperm motility, morphology, and DNA integrity. However, its effect on downstream embryological outcomes remains insufficiently explored. This study aims to evaluate whether PRP incubation prior to ICSI improves blastocyst formation and embryo quality.

2. Objectives

Primary Objective:

To evaluate the effect of PRP incubation on blastocyst formation rate in ICSI cycles involving low-quality sperm

Secondary Objectives:

- To assess fertilisation rate
- To assess cleavage rate
- To evaluate blastocyst quality (good, fair, poor)

3. Study Design

This study is a prospective, randomized controlled study conducted at Halim Fertility Center, Stella Maris Women's and Children's Hospital, Medan, Indonesia, between January 2023 and August 2023.

Participants were recruited using consecutive sampling. Couples undergoing more than one IVF-ICSI cycle were excluded.

4. Participants

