6.1 PRP Group

Sperm samples were incubated with autologous PRP for one hour prior to ICSI. PRP was prepared from 10 mL peripheral blood using a two-step centrifugation process. A ratio of 30 μ L PRP to 0.3 mL sperm (10% v/v) was used.

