6.2 Control Group

Standard sperm preparation without PRP incubation.

All samples underwent density gradient centrifugation prior to intervention.

7. Ovarian Stimulation and ICSI Procedure

Female partners underwent controlled ovarian stimulation using a GnRH antagonist protocol. Oocyte retrieval was performed 35–36 hours after hCG trigger. Mature oocytes (MII) were inseminated using ICSI 38–42 hours post-trigger.

8. Embryo Culture and Assessment

Fertilisation assessed at 17 ± 1 hours (2PN). Cleavage assessed on day 3. Blastocyst assessed on day 5.

Blastocysts were graded using the Gardner classification:

Good: AA

Fair: AB, BA, BB

Poor: AC, CA, BC, CB, CC

All assessments were performed by a single blinded embryologist.

9. Outcome Measures

Primary Outcome:

Blastocyst formation rate

Secondary Outcomes:

Fertilisation rate

Cleavage rate

Blastocyst quality

10. Statistical Analysis Plan

Statistical analysis was conducted using SPSS version 21.0 (IBM Corp., Armonk, NY, USA).

Normality assessed using Shapiro–Wilk test

Continuous variables analysed using Student's t-test or Mann–Whitney U test

Categorical variables analysed using Chi-squared test

Data presented as mean \pm standard deviation (SD) or median (IQR)

Categorical data presented as percentages (%)

Statistical significance set at $P < 0.05$

No adjustment for multiple comparisons was performed as outcomes were pre-specified.

Rumah Sakit Ibu & Anak
STELLA MARIS
Women's & Children's Hospital
KLINIK BAYI TABUNG HALIM FERTILITY CENTER
[name]
Telp : [name], [contact]

11. Ethical Considerations

The study was approved by the Institutional Ethics Committee of Stella Maris Women's and Children's Hospital (Approval No. 608.1/Dir/RSIA.SM/XII/2022; approved on 19 December 2022).

Written informed consent was obtained from all participants prior to enrolment.

12. Data Confidentiality

All participant data were anonymized and handled in accordance with ethical and regulatory standards. No identifiable personal data are included in this document.

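### The primary outcome, blastocyst formation rate, has no numerator, denominator or unit of analysis, and two of the candidate denominators arise after PRP treatment and may be affected by it

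*Combined protocol and SAP*

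**What the plan says.** The primary objective (section 2) is "To evaluate the effect of PRP incubation on blastocyst formation rate in ICSI cycles involving low-quality sperm". Section 9 repeats the term as the primary outcome, "Blastocyst formation rate", and adds nothing to it.

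Section 8 gives times of assessment but no ratios: "Fertilisation assessed at 17 ± 1 hours (2PN). Cleavage assessed on day 3. Blastocyst assessed on day 5". Section 7 supplies a further possible denominator without using it as one: "Mature oocytes (MII) were inseminated using ICSI 38–42 hours post-trigger".

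On the order of events, section 6.1 states: "Sperm samples were incubated with autologous PRP for one hour prior to ICSI". Fertilisation rate and cleavage rate are secondary outcomes.

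Section 10 assigns t-tests or Mann–Whitney tests to continuous variables and chi-squared tests to categorical ones. It does not say which kind of variable the primary rate is. It also gives pre-specification of the outcomes as the reason for making no multiplicity adjustment.

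**The concern.** A rate is not defined until its numerator, denominator and unit are. Here at least three denominators can be read from the plan: MII oocytes, 2PN zygotes and day-3 cleaved embryos. The unit could be the couple or the pooled embryo.

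The choice is not neutral. The sperm are treated before injection, so the 2PN and cleaved counts come after the intervention, and the plan itself sets out to measure whether they differ between arms. Dividing by either count restricts the comparison to embryos that got past a stage PRP may influence. The two sets of embryos are then no longer comparable by virtue of allocation.

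Total fertilisation failure, the worst embryological result, also goes uncounted. On a per-couple 2PN rate such a couple is 0/0. On a pooled 2PN rate it adds nothing to numerator or denominator.

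At stake is the stated aim: "This study aims to evaluate whether PRP incubation prior to ICSI improves blastocyst formation and embryo quality". With the denominator open, the version reported can be chosen after the data are seen, and section 10's appeal to pre-specification does not hold for the primary outcome.

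**Working it through.** The documents state no rate, effect size or sample size, so there is no figure of the plan's to reproduce. Every rate below is an assumption used to test how the result depends on the denominator.

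**Notation.** f = 2PN per MII, c = cleaved per 2PN, b = blastocysts per cleaved embryo. Then blastocysts per MII = f·c·b, per 2PN = c·b, per cleaved embryo = b.

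**When the sign differs between per-MII and per-2PN.** Let R = (c·b in PRP) / (c·b in control). The per-MII ratio is R·fP/fC, where fP and fC are the values of f in the PRP and control arms.
- If PRP raises fertilisation, the signs differ only when fC/fP < R < 1.
- If PRP lowers fertilisation, they differ only when 1 < R < fC/fP.
- If fP = fC the band is empty. If c is also equal, all three denominators give the same sign.

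For fC = 0.60 and fP = 0.65, 0.70 or 0.75, the band for R is (0.923, 1), (0.857, 1) or (0.800, 1).

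**Example of reversal, more fertilisation.** Control: f = 0.60, with 45% of 2PN reaching blastocyst. PRP adds 10 points of fertilisation, and the added zygotes reach blastocyst at 25%.
- Per MII: 0.60 × 0.45 = 27.0%; 0.270 + 0.10 × 0.25 = 29.5%.
- Per 2PN: 45.0%; 0.295 / 0.70 = 42.1%.
- R = 0.421 / 0.45 = 0.937, inside (0.857, 1).

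**Example of reversal, less fertilisation.** PRP loses 10 points of fertilisation from zygotes that would have reached blastocyst at 10%.
- Per MII: 27.0%; 0.270 − 0.10 × 0.10 = 26.0%.
- Per 2PN: 45%; 0.260 / 0.50 = 52%.
- R = 0.52 / 0.45 = 1.156, inside (1, 1.2).

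**Further scenarios, PRP minus control, in percentage points**

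| Assumed f, c, b (control; PRP) | Per MII | Per 2PN | Per cleaved | Sign |
|---|---|---|---|---|
| 0.60, 0.95, 0.45; 0.75, 0.95, 0.42 | +4.3 | −2.9 | −3.0 | reverses |
| 0.65, 0.90, 0.45; 0.65, 0.90, 0.50 | +2.9 | +4.5 | +5.0 | same |
| 0.60, 0.90, 0.45; 0.66, 0.92, 0.50 | +6.1 | +5.5 | +5.0 | same |

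The second row has equal fertilisation and cleavage: the sign holds, but the absolute difference still varies from 2.9 to 5.0 points. In the third row both later denominators change and the sign still holds.

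**Couples with no 2PN.** Assume a beta-binomial model with ICC 0.15. Then α + β = (1 − 0.15)/0.15 = 5.667, β = (1 − f) × 5.667, and with n MII oocytes P(no 2PN) is the product over i = 0 to n − 1 of (β + i)/(5.667 + i). Averaging over the number of MII oocytes (mean 8, couples with at least one) gives:

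| MII count | f = 45% | f = 55% | f = 65% |
|---|---|---|---|
| exactly 8 | 5.6% | 2.4% | 0.9% |
| Poisson | 7.4% | 3.7% | 1.8% |
| negative binomial, size 3 | 11.7% | 7.3% | 4.4% |

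The range is roughly 1–12% and depends heavily on the spread of MII counts, which the documents do not give.

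**The case against.** A reader might infer that PRP does change the number of 2PN and cleaved embryos. The documents do not say so: they list fertilisation and cleavage as outcomes to be assessed, and section 1 describes the effect on embryo outcomes as little explored. Only the statement that these counts may be affected is supported.

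A reader might also infer that a shift in the denominator is enough to reverse the result. It is not. The conditional blastocyst rate must move the opposite way, and within the band shown above; with a small gain in fertilisation (0.60 to 0.65) that band is narrow. The reversing examples are possibilities under assumed rates, not predictions.

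It is fair to add that MII oocytes are not the only denominator beyond PRP's reach. Retrieved oocytes and the allocated couple are equally unaffected. Injection follows the incubation, so the number of oocytes actually injected is, strictly, a post-treatment count; the number available is not. A per-MII rate also has its own 0/0 case, the couple with no MII oocyte. The 0/0 problem for couples with no 2PN applies only if the rate is taken per couple.

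Finally, a per-2PN rate answers a legitimate question about embryo development once fertilised. That is a reason to report it, not a reason to leave the primary outcome undefined. The omission and the selection after allocation both stand.

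**Conclusion.** The point holds as a definition gap with consequences for bias. The gap itself is certain: no section gives a numerator, denominator or unit. That 2PN and cleaved counts follow treatment is also clear from the order of procedures. From these it follows that the plan permits a primary comparison between embryos selected after allocation, with the choice open until the data are known.

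The size is conditional. The magnitude of the effect varies with the denominator in every scenario tried. The sign varies only where the per-2PN rate runs against fertilisation inside the stated band, and not at all when fertilisation and cleavage are equal between arms. The loss of couples with no 2PN cannot be fixed from the documents; 1–12% rests on assumed fertilisation of 45–65%, a mean of 8 MII and ICC 0.15. The documents do not support a claim that the result will reverse, or a single figure for the share of couples lost.

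**What to change.** In sections 2, 9 and 10, define the primary outcome as the number of day-5 blastocysts divided by the number of MII oocytes available for injection, summarised per allocated couple. Count couples with no fertilisation or no blastocyst as zero, and state a rule for couples with no MII oocyte. Name the test that applies to this quantity.

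Report per-2PN and per-cleaved rates as supportive, labelled as conditional on a post-treatment event.

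The plan is written in the past tense and gives January to August 2023 as the study period. If data are already collected, report the rate under all denominators and say when the primary one was chosen.

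The cost is mainly wording. The counts should be available from the procedures in sections 7 and 8, although the plan does not say outright that MII numbers are recorded. The downside is a headline percentage lower than a per-2PN rate and less directly comparable with rates reported per 2PN.

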4.1 Inclusion Criteria (Male)

- Sperm concentration <5 million/mL
- Total motility <42%
- Normal morphology <4%
- Provided informed consent

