4.3 Exclusion Criteria (Female)

- Age ≥ 40 years
- Polycystic ovarian syndrome (Rotterdam criteria)
- Low ovarian reserve (AFC <5 or AMH <0.5–1.1 ng/mL)

5. Randomisation and Blinding

Participants were randomly allocated into two groups using registration number parity:

Odd numbers: PRP group

Even numbers: Control group

Embryologists performing ICSI and outcome assessments were blinded to group allocation.

6. Interventions

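### Only unadjusted two-group tests are planned, although female age and baseline sperm values are known for every couple and could be pre-specified as covariates

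*Combined protocol and SAP*

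**What the plan says.** Section 10 (Statistical Analysis Plan) gives one line for each type of outcome: "Continuous variables analysed using Student's t-test or Mann–Whitney U test" and "Categorical variables analysed using Chi-squared test". None of these tests takes a covariate. The section names no regression model, analysis of covariance, stratified test or adjusted sensitivity analysis. Its only sentence on adjustment, "No adjustment for multiple comparisons was performed as outcomes were pre-specified", is about multiplicity.

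The primary outcome in section 9 is "Blastocyst formation rate", with no stated denominator or unit of analysis.

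Section 4.1 admits men on three semen values, among them "Sperm concentration <5 million/mL" and "Total motility <42" per cent; the third is normal morphology. Section 4.3 excludes women aged 40 or over and women with "Low ovarian reserve (AFC <5 or AMH <0.5–1.1 ng/mL"). Section 5 allocates by odd or even registration number and mentions no stratification. No sample size is stated.

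**The concern.** Female age and the three semen values must be known for every couple before eligibility can be decided, so they are available as baseline covariates. The protocol gives its own reasons to expect some of them to matter. Section 1 links poor sperm quality to impaired fertilisation and lower blastocyst formation, and section 4.3 removes older women and women with low ovarian reserve. The design restricts the range of these factors but does not balance what remains of them between arms, and the analysis does not account for it.

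Two things are at stake. Outcome variation that the covariates could explain stays in the error term and widens the confidence interval. A chance difference between arms in, say, female age also goes uncorrected. In addition, with no adjustment fixed in advance, a baseline table that shows a difference invites adjustment chosen after the fact.

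**Working it through.** The plan states no sample size, effect size, SD or R², so it has no figure to reproduce. Everything below rests on assumed values, shown over a range.

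**Precision.** In a linear model of a couple-level outcome, covariates explaining a share R² of the variance multiply the standard error by √(1 − R²). The equivalent gain in sample size is 1/(1 − R²) − 1.

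| R² (assumed) | SE multiplier | Equivalent gain in couples |
|---|---|---|
| 0.02 | 0.990 | 1/0.98 − 1 = 2% |
| 0.10 | 0.949 | 1/0.90 − 1 = 11% |
| 0.20 | 0.894 | 1/0.80 − 1 = 25% |

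In terms of power, take an assumed standardised effect of 0.5, two-sided alpha 0.05 and 63 couples per arm, which gives 80.1% unadjusted. Adjustment raises this to 80.9%, 84.1% and 88.1% at the three R² values.

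**Few embryos per couple.** If the covariates explain a share of the true between-couple variance only, binomial noise in each couple's rate stays unexplained. Assume 6 embryos per couple and an intra-couple correlation of 0.10. The between-couple share of the variance of an observed rate is then 0.10/(0.10 + 0.90/6) = 0.10/0.25 = 0.40.

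- Explaining 10% of the between-couple part gives an effective R² of 0.40 × 0.10 = 0.04, and a gain of 1/0.96 − 1 = 4%.
- Explaining 20% gives 0.40 × 0.20 = 0.08, and a gain of 1/0.92 − 1 = 9%.

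**Chance imbalance.** Under true randomisation with n couples per arm, the standardised difference d between arms in one covariate has SD √(2/n). If that covariate carries all of R², the unadjusted estimate shifts by √R² × d outcome SDs. The type I error of the unadjusted test, given d, follows from a normal approximation with conditional standard error √(2/n) × √(1 − R²). With an assumed female-age SD of 4 years, 0.25 SD is 1 year and 0.5 SD is 2 years.

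| n per arm (assumed) | Imbalance exceeded | Probability | Type I error at that imbalance, R² = 0.10 | Same, R² = 0.20 |
|---|---|---|---|---|
| 30 | 0.25 SD | 33% | 4.9% | 4.8% |
| 30 | 0.5 SD | 5.3% | 8.1% | 11.1% |
| 40 | 0.25 SD | 26% | 5.3% | 5.4% |
| 40 | 0.5 SD | 2.5% | 9.6% | 14.2% |

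The shift at 0.25 SD is √0.10 × 0.25 = 0.08 to √0.20 × 0.25 = 0.11 outcome SDs. At 0.5 SD it is 0.16 to 0.22. A 1-year age gap is therefore common but leaves the error rate near 5%. A 2-year gap matters but is uncommon when allocation is random.

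**The case against.** The strongest reply is that an unadjusted comparison is valid under sound randomisation, so this is a matter of efficiency and not an error. That stands. A reader might infer from the missing covariates that the planned tests are biased, or that a small age difference would materially distort the PRP estimate. The documents do not support either reading, and the working above shows a 1-year gap to be close to harmless.

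Further limits also stand:

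- R² may be small, because eligibility caps female age below 40 and confines the semen values to a narrow low range. That is why the range above starts at 0.02.
- A reader might say that the plan marks the sperm values as prognostic by excluding their extremes. It does not: section 4.1 lists them as inclusion criteria, and they define the population. Only the female criteria are exclusions. The support for sperm quality as prognostic comes from section 1.
- Section 4.3 joins AFC and AMH with "or", so it does not show that either measure exists for every couple.
- The 1/(1 − R²) formula belongs to a linear model. In a logistic model the adjusted odds ratio is a different estimand and its standard error need not shrink.
- Odd/even allocation is predictable. Adjusting for measured covariates does not remove selection on unmeasured ones.
- The document is written in the past tense. If outcomes were already known, promoting an adjusted model to primary would be a post hoc choice.

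None of this removes the omission. Female age and sperm concentration are available for all couples, and using them requires no new measurement.

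**Conclusion.** The point holds as a recommendation on efficiency and robustness. Every comparison in section 10 is unadjusted, although female age and baseline sperm values must be on record for each couple and allocation is unstratified.

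The gain from adjustment runs from about 2% to 25% more couples for R² between 0.02 and 0.20 in a linear couple-level model. It falls to about 4% to 9% if 10% to 20% of only the between-couple variance is explained, with 6 embryos per couple and a correlation of 0.10. All these inputs are assumptions, so the documents settle the direction of the loss but not its amount. Protection against imbalance is a real but modest benefit: serious imbalance in any one covariate is uncommon under true randomisation at 30 to 40 couples per arm. Predictable allocation could make it more frequent, but that is a separate problem with its own remedy.

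**What to change.** Add to section 10, for the blastocyst formation rate:

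- A couple-level model, or a model clustered on couple, with arm, female age (continuous) and baseline sperm concentration.
- AMH or AFC as a further covariate only if the chosen measure is confirmed as recorded for all couples.
- A named effect measure, for example the adjusted difference in rate with its 95% CI.
- The unadjusted result as a sensitivity analysis.
- The same covariates for fertilisation, cleavage and blastocyst quality.
- A statement that covariates are not selected by significance tests on baseline data.

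If outcome data have already been seen, report the adjusted analysis as a labelled sensitivity analysis and do not make it primary.

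The cost is SAP wording and somewhat more modelling work, including a stated unit of analysis for each outcome, which the plan lacks. No new data are needed for the two core covariates. The change does not repair selection on unmeasured factors under odd/even allocation.

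### The plan does not fix the unit of analysis for outcomes recorded on several embryos per couple, and any chi-squared test on pooled embryos would give P values that are too small

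*Combined protocol and SAP*

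**What the plan says.** Section 2 states the primary objective as: "To evaluate the effect of PRP incubation on blastocyst formation rate in ICSI cycles involving low-quality sperm". Section 9 lists the primary outcome simply as "Blastocyst formation rate", with no denominator and no unit.

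On the unit of allocation, Section 5 says "Participants were randomly allocated into two groups using registration number parity", and Section 3 adds "Couples undergoing more than one IVF-ICSI cycle were excluded". Each couple therefore contributes one cycle, and all its oocytes belong to one arm.

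The outcomes arise below that level. Section 7 describes injection of mature oocytes. Section 8 describes checks for fertilisation, cleavage and blastocyst stage, and then "Blastocysts were graded using the Gardner classification", collapsed to good, fair or poor.

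Section 10 gives two rules for comparing the arms: "Continuous variables analysed using Student's t-test or Mann–Whitney U test" and "Categorical variables analysed using Chi-squared test", with normality checked by Shapiro–Wilk and significance at 0.05. It does not say which rule covers the three rates. It names no mixed model, GEE, robust standard error or other method for correlated observations, and it asks for no effect estimate or confidence interval.

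**The concern.** Oocytes from one couple share an egg source, a sperm sample and, in the PRP arm, a single incubation. Their outcomes are likely to be positively correlated. An ordinary chi-squared test on pooled embryos counts each embryo as independent evidence, so its standard error is too small and it rejects a true null more often than 5%.

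Two things are at stake. First, blastocyst grade is categorical and given to each blastocyst, the only categorical test is chi-squared, and no per-couple summary of grade is defined. Followed as written, the plan leads most naturally to a pooled table. Second, the primary rate can be analysed either way: as pooled counts by chi-squared, or as a per-couple percentage by t-test or Mann–Whitney. These routes have different error rates, and nothing stops the choice being made after the data are seen. Section 10 justifies leaving multiplicity unadjusted because the outcomes were fixed in advance, but the analysis of the primary outcome was not.

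**Working it through.** **Inputs from the documents.** Nominal alpha 0.05 (Section 10); allocation by participant, taken here as the couple (Section 5); one cycle per couple (Section 3). There is no sample size, power, event count or other figure to reproduce.

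**Inputs assumed.** Embryos per couple *m*, intracluster correlation (ICC), couples per arm and event rate are not in the documents. They are varied below.

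**Step 1: formula for a two-group comparison of pooled embryos, equal cluster sizes.**
DEFF = 1 + (*m* − 1) × ICC
True alpha = 2 × [1 − Φ(1.96 / √DEFF)]

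Check: with *m* = 1 or ICC = 0, DEFF = 1 and the formula returns 5.0%.

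Example: *m* = 8, ICC = 0.10. DEFF = 1 + 7 × 0.10 = 1.70; √1.70 = 1.304; 1.96 / 1.304 = 1.503; two-sided tail = 13.3%. A correct confidence interval would be about 1.3 times as wide as the pooled one.

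| Embryos per couple | ICC 0.02 | ICC 0.05 | ICC 0.10 | ICC 0.20 |
|---|---|---|---|---|
| 2 | 5.2% | 5.6% | 6.2% | 7.4% |
| 3 | 5.5% | 6.2% | 7.4% | 9.8% |
| 5 | 5.9% | 7.4% | 9.8% | 14.4% |
| 8 | 6.6% | 9.2% | 13.3% | 20.6% |
| 10 | 7.1% | 10.4% | 15.5% | 24.2% |

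**Step 2: simulation with varying numbers per couple.** Beta-binomial data under no effect, 40 couples per arm, 40% rate, Poisson-type cluster sizes, 4,000 runs. Pooled chi-squared at nominal 5% rejected as follows:

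| Mean per couple | ICC 0.05 | ICC 0.10 | ICC 0.20 |
|---|---|---|---|
| 3 | 6.6% | 7.8% | 10.9% |
| 5 | 7.8% | 10.9% | 16.8% |
| 8 | 9.7% | 14.2% | 23.9% |

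These run slightly above the formula because unequal clusters add to the design effect. Results with 20 couples per arm are similar (for example 11.8% at mean 5, ICC 0.10, and 22.4% at mean 8, ICC 0.20).

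A second simulation (10,000 runs, 40 couples per arm, 35% rate, more variable negative-binomial cluster sizes) gave about 6% at mean 2 to 3 and ICC 0.02, rising to about 28% at mean 10 and ICC 0.20.

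**Step 3: blastocyst grade.** For the 2 × 3 table (2 degrees of freedom, common design effect), true alpha = 0.05^(1/DEFF).
- *m* = 2, ICC 0.10: DEFF = 1.10, giving 6.6%.
- *m* = 3, ICC 0.10: DEFF = 1.20, giving 8.2%.
- *m* = 3, ICC 0.20: DEFF = 1.40, giving 11.8%.

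Allowing for unequal numbers of blastocysts, about 7% to 10% is a fair range at 2 to 3 per couple and ICC 0.10.

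**Step 4: the couple as unit.** In the first simulation (both couple numbers, mean 3 to 8, ICC 0 to 0.20), comparing per-couple rates gave a type I error of 4.0% to 5.5% for the t-test and 3.7% to 5.8% for Mann–Whitney, with simulation error of about 0.3 to 0.6 points. In the second, the t-test gave 4.4% to 5.2%.

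**The case against.** The strongest reply is that the plan never says embryos will be pooled. A blastocyst formation rate can be a percentage for each couple, summarised by mean and SD or median and IQR as Section 10 allows, and compared by t-test or Mann–Whitney. Step 4 shows that this route holds its level. This stands. A reader might infer that the plan commits the primary outcome to a test with a false-positive rate well above 5%; the text does not support that. It leaves the route open, which is a defect of a different kind.

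The same caution applies to grade. Pooling is the natural reading, but a per-couple proportion of good blastocysts, or a best grade, is not ruled out. Inflation there is also smaller, because there are likely to be few blastocysts per couple.

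The size rests wholly on assumed inputs. With few embryos per couple and a low correlation, the error is barely above 5%.

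Finally, equal weighting of couples is a legitimate choice when couples are allocated. It may cost efficiency, but no type I error problem was found for it, and none was demonstrated for the Shapiro–Wilk step. A GEE or mixed model is therefore one adequate remedy and not the only one.

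What remains is that one permitted route is sound, another is not, and the plan does not choose.

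**Conclusion.** The concern holds in a conditional form. The documents establish that couples are allocated, that outcomes arise on several embryos per couple, that the unit of analysis and denominators are undefined, and that nothing provides for clustering. If chi-squared is applied to pooled oocytes or embryos, P values are too small for any positive within-couple correlation. Only the amount is uncertain: about 6% to 28% in place of 5% over mean 2 to 10 embryos per couple and ICC 0.02 to 0.20, with 40 couples per arm and a 35% rate, all assumed.

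The documents do not show that the primary P value will be wrong, nor that pooling is certain for grade. The point still needs correcting before the results are relied on, because the primary test cannot be identified from the plan and one permitted reading of it is invalid.

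**What to change.** In Section 9, state one denominator for each rate (for example oocytes injected, fertilised oocytes or cleaved embryos); the choice is the sponsor's, but it must be fixed.

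In Section 10, name one primary analysis that treats the couple as the unit. Either of these is adequate:
- a logistic GEE or mixed model with arm as factor and couple as cluster, with small-sample-corrected standard errors; or
- a comparison of per-couple rates by one test named in advance, not selected by Shapiro–Wilk.

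Report the difference in rates, or the odds ratio, with a 95% confidence interval. Use the same approach for fertilisation and cleavage, and a clustered ordinal or couple-level analysis for grade. Restrict chi-squared to variables with one value per couple.

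The cost is SAP wording and somewhat wider intervals than a pooled analysis would show. No new data are needed, and SPSS, which the plan already names, has procedures for clustered models (GENLIN, GENLINMIXED).
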